Copyright © 2009, 2010, 2012, 2016, 2018 IQVIA. All rights reserved. The contents of this document are confidential and proprietary to IQVIA Holdings Inc. and its subsidiaries. Unauthorized use, disclosure or reproduction is strictly prohibited.

MODIFICATION HISTORY

Unique Identifier for this Version	Date of the Document Version	Author	Significant Changes from Previous Authorized Version
1.0	05APR2019	██████████	Not Applicable – First Version
2.0	29OCT2019	██████████	
 - Patient profiles and TLF shells now in separate documents - Updates following Debiopharm review of the list of TLFs and corresponding shells - Updates to be in line with protocol version 3
3.0	17NOV2020	██████████	
Section 5.5 Added for the extended period after the protocol amendment 3
 
Section 6.5 Efficacy Analysis Set:
 
 - treatment failure definition updated to take into account Covid-19 impact - Add details on the criteria for the definition of Efficacy population (7 categories) 
Section 10.1 Subject Disposition:
 
categories added in the summary table
 
Section 13 Prior Anti-Cancer Treatments:
 
added a listing for prior and current anti-cancer treatments
 
Section 16.1 Derivation:
 
Planned cumulative dose definition has been updated
 
Section 17.2.1.5 Progression-free survival (PFS): censoring rules more detailed, adding death due to COVID-19.
 
Section 17.2.4 Sensitivity Analysis of Secondary Efficacy:
 
Variables Another sensitivity analysis will be performed by censoring the OS at the time of death due to COVID-19.

Document: T:\sas\Debiopharm\Debio_1143\CZA60507\Biostatistics\Documentation\SAP\SAP Text\V5

Author: ██████████

Version Number: 5.0

Version Date: 19APR2022

Template No.: CS_TP_BS016 Revision 5
Effective Date: 01Apr2018

Reference: CS_WI_BS005

			
Section 18.1.14 TEAEs leading to death: Additional listing added for all AEs leading to death

V4.0	29JUL21	██████████	
Formula for derivation of Duration of exposure updated in section 15.1. Compliance derivations updated in section 16. Mention that Efficacy population is not applicable for Part A in section 6.5. Update the wording of “Critical deviations” by “Major deviations” In section 10.2. Update the definition of Medical History in section 12. Mention in section 4.3 that no pooling of part A and Part B will be performed.

V5.0	19APR2022	██████████	
Section 6 Analysis Set:
 
 - Clarify that efficacy analysis set is a subset of ITT - Clarify that RP2D is not applicable for Part B - Clarify that any patient with one of the deviation described in category 5 will be automatically excluded from Efficacy population - Clarify that category 7 corresponds to patients whose treatment had to be delayed or interrupted for reasons related to COVID-19 pandemic only and did not receive at least 25% of the planned Debio1143 dose or didn't receive any dose of nivolumab infusion during cycle 1 
Section 7.6 Statistical Test:

Document: T:\sas\Debiopharm\Debio_1143\CZA60507\Biostatistics\Documentation\SAP\SAP Text\V5

Author: ██████████

Version Number:

5.0

Version Date:

19APR2022

Template No.: CS_TP_BS016 Revision 5

Effective Date: 01Apr2018

Reference: CS_WI_BS005

			
 - Update the rounding rules for quantitative summaries, to not have irrelevant decimales 
Section 14 Medications
 
 - Update the definition of Concomitant medications 
Section 18.1.15 Most common TEAE
 
 - Clarify that AEs where the overall percentage is $\geq 5\%$ will also be summarized by SOC and PT 
Section 18.5.1 Vital Signs Markedly Abnormal Criteria
 
 - Low and High Markedly Abnormal Criteria updated for Weight 
Section 20 Pharmacodynamics
 
 - Update the definition of On-treatment period 
Typo corrected throughout all the document

--	--	--	----------------------------------------------------------------------------------------------------------------------------------------------------------------------------------------------------------------------------------------------------------------------------------------------------------------------------------------------------------------------------------------------------------------------------------------------------------------------------------------------------------------------------------------------------------------------------------------------------------------------------------------------------------------------------------------------------------------------------------------------------------------------------------------------------------------------------------------------------------

1. INTRODUCTION

This document describes the rules and conventions to be used in the presentation and analysis of efficacy, safety, pharmacokinetic (PK), pharmacodynamic (PDy), and genetic data for Protocol Debio 1143-106. It describes the data to be summarized and analysed, including specifics of the statistical analyses to be performed.

This statistical analysis plan (SAP) is based on protocol version 4 dated 03rd April 2020. This SAP will cover analyses for both part A (phase 1b) and part B (phase 2).

Document:	T:\sas\Debiopharm\Debio_1143\CZA60507\Biostatistics\Documentation\SAP\SAP Text\V5	Version Number:	5.0
Author:	██████████	Version Date:	19APR2022

Template No.: CS_TP_BS016 Revision 5
Effective Date: 01Apr2018

Reference: CS_WI_BS005

2. STUDY OBJECTIVES

2.1. PRIMARY OBJECTIVE

2.1.1. PART A

The primary objective of the dose-optimization part of the study is to determine the recommended phase 2 dose (RP2D) taking into account dose limiting toxicities (DLTs) in Cycle 1, overall safety/tolerability and PK, by optimizing doses of Debio 1143 when combined with the standard dose of nivolumab, as well as treatment compliance in patients with advanced solid malignancies who failed prior systemic standard treatments.

2.1.2. PART B

The primary objective of the basket trial is to evaluate the preliminary anti-tumour activity of Debio 1143 at the RP2D in combination with nivolumab at the standard dose, overall and in each patient cohort.

2.2. SECONDARY OBJECTIVES

2.2.1. PART A

For the dose-optimization part, secondary objectives are to assess the:

1. PK disposition of Debio 1143 (including its metabolite Debio 1143-MET1) and nivolumab when administered in combination.
2. Anti-tumour activity of Debio 1143 in combination with nivolumab in patients with advanced solid malignancies.

2.2.2. PART B

For the basket trial, secondary objectives are to assess the:

1. Safety and tolerability of the RP2D of Debio 1143 when given in combination with nivolumab in patients with advanced solid malignancies.
2. PK disposition of Debio 1143 (and its metabolite Debio 1143-MET1) and nivolumab when administered in combination.

2.3. EXPLORATORY OBJECTIVES

The exploratory objectives of this study are:

1. To explore potential predictive and PDy biomarkers of Debio 1143 and nivolumab when administered in combination, in blood and tumour tissue, [REDACTED]
[REDACTED]
[REDACTED]
2. To explore genetic variations in drug metabolism enzyme and transporter (DMET) genes associated with differences in the PK disposition of Debio 1143 in combination with nivolumab
3. To explore the exposure/response relationship for efficacy and safety (including PK/PDy correlations, if applicable) of Debio 1143 in combination with nivolumab
4. To explore correlations between response, clinical parameters, immune correlates, and putative biomarkers, [REDACTED]
5. To explore the relationship between Debio 1143 plasma concentrations and QTcF

3. STUDY ENDPOINTS

3.1. PRIMARY ENDPOINTS

3.1.1. PART A

The primary endpoint of part A is the RP2D of Debio 1143 when combined with the standard dose of nivolumab, in patients with advanced solid malignancies who received prior systemic standard treatment and failed a prior PD-1/PD-L1-containing treatment, as per DLT occurrence in less than one-third of evaluable treated patients at the RP2D dose level.

3.1.2. PART B

The primary endpoint of part B is the confirmed objective response rate (ORR) as per Response Evaluation Criteria in Solid Tumor (RECIST) v1.1 and/or Gynecologic Cancer Intergroup (GCIG) criteria (Cohort 4, if applicable).

Document: T:\sas\Debiopharm\Debio_1143\CZA60507\Biostatistics\Documentation\SAP\SAP Text\V5

Author: [REDACTED]

Version Number:

5.0

Version Date:

19APR2022

Template No.: CS_TP_BS016 Revision 5

Reference: CS_WI_BS005

Effective Date: 01Apr2018

3.2. SECONDARY ENDPOINTS

Secondary endpoints for both study parts (unless otherwise specified) are:

- Incidence and severity of treatment-emergent adverse events (TEAEs) and clinical laboratory abnormalities, according to National Cancer Institute-Common Terminology Criteria for Adverse Events NCI-CTCAE version 5.0 criteria
- Changes in vital signs: systolic/diastolic blood pressure, heart rate (both after at least 5 minutes of supine rest), temperature, and weight; electrocardiogram (ECG) and Eastern Cooperative Oncology Group Performance Status (ECOG-PS)
- Incidence of premature treatment discontinuations and treatment modifications due to TEAEs and laboratory abnormalities (i.e., treatment compliance)
- Tumor response determined according to RECIST v1.1 and/or GCIG criteria (Cohort 4, if applicable):
 - Confirmed (Part A) and unconfirmed (Parts A and B) ORR
 - Disease control rate (DCR), defined as any response, partial or complete (PR or CR) + stable disease (SD)
 - Time-related endpoints as median time to response, median duration of response (DOR), median progression-free survival (PFS), PFS rate every months, median overall survival (OS), OS rate at 12 months and 18 months (if data allow)
- PK parameters of Debio 1143 and Debio 1143-MET1 as defined in the available population PK disposition model and, if appropriate, post-hoc estimates of areas under the curve (AUCs), C_{max}, and C_{min}; serum concentration versus time profiles of nivolumab and, if deemed appropriate, relevant nivolumab PK parameters derived from a population PK model.

3.3. EXPLORATORY ENDPOINTS

Exploratory endpoints are:

- Potential predictive (*) and PDy biomarkers of Debio 1143 combined with nivolumab, in blood and tumor tissue [REDACTED]
- Best overall response (BOR) evaluation using the novel iRECIST 2017 guideline for immunotherapeutics
- Correlations between PK disposition of Debio 1143 combined with nivolumab and clinical response and/or any tumor metrics

Document: T:\sas\Debiopharm\Debio_1143\CZA60507\Biostatistics\Documentation\SAP\SAP Text\V5

Author: [REDACTED] Version Number: 5.0
Version Date: 19APR2022

Template No.: CS_TP_BS016 Revision 5
Effective Date: 01Apr2018

Reference: CS_WI_BS005

- Correlations between PK disposition of Debio 1143 combined with nivolumab and safety profile, and PDy if applicable
- Correlations between Debio 1143 and Debio 1143-MET1 plasma concentrations and changes from baseline in QTc interval as corrected by Fridericia (QTcF).
- Correlations between response, clinical parameters, immune correlates and putative biomarkers, [REDACTED]
- Genetic variations in DMET genes associated with differences in the PK disposition of Debio 1143 in combination with nivolumab (*).

(*) – the analysis of these endpoints will be described in a separate analysis plan.

4. STUDY DESIGN

4.1. GENERAL DESCRIPTION

4.1.1. PART A

Part A has an open-label, multicentre dose-optimization design applying the classical 3+3 method, aiming at optimizing the Debio 1143 dose in combination with standard doses of nivolumab (OPDIVO®) to determine the RP2D taking into account safety/tolerability and PK, as well as the treatment compliance in pre-treated patients with advanced solid malignancies.

Eligible patients will enter Part A of the study in cohorts of three evaluable patients. The starting dose of Debio 1143 will be 150 mg, daily, administered orally for 10 consecutive days every 2 weeks (i.e., Days 1-10 and Days 15-24 inclusively of each 28-day cycle [q4w]). The dose will be optimized according to the observed DLTs, patient treatment compliance, safety/tolerability and PK data, if applicable.

The DLT period is defined as Cycle 1 (i.e. lasting 4 weeks or longer in case of dosing delays). Treatment-related toxicities fulfilling DLT criteria but occurring after Cycle 1 (i.e., delayed DLTs) may also be considered for RP2D definition after discussion and agreement between the Investigators, Data Safety Monitoring Committee (DSMC) and the sponsor.

Nivolumab will be administered at 240 mg (flat dose) over at least 30 minutes as an IV infusion on Days 1 and 15 of a 28-day cycle. From Cycle 3, patients may be switched to nivolumab at a dose of 480 mg IV over at least 60 minutes on Day 1 q4w, exclusively upon Investigator request with the Sponsor agreement.

Document: T:\sas\Debiopharm\Debio_1143\CZA60507\Biostatistics\Documentation\SAP\SAP Text\V5

Author: [REDACTED] Version Number: 5.0
Version Date: 19APR2022

Template No.: CS_TP_BS016 Revision 5
Effective Date: 01Apr2018

Reference: CS_WI_BS005

Copyright © 2009, 2010, 2012, 2016, 2018 IQVIA. All rights reserved. The contents of this document are confidential and proprietary to IQVIA Holdings Inc. and its subsidiaries. Unauthorized use, disclosure or reproduction is strictly prohibited.

The maximum explored Debio 1143 dose will be 200 mg/day. Neither Debio 1143 dose escalation beyond this threshold nor any nivolumab dose increases are foreseen in this study. In individual cases of severe toxicity, the Debio 1143 dose may be reduced by a maximum of two decrements of 50 mg/day or up to a minimum dose of 100 mg/day.

According to the 3+3 dose-optimization design, if none of the three evaluable patients at the starting dose cohort experiences a DLT during Cycle 1, three more patients will be treated at the next dose level. However, if one of the first 3 evaluable patients experiences a DLT during the DLT period, 3 more patients will be treated at the same dose level. If ≤ 1 out of 6 evaluable patients experiences a DLT during the first cycle, at the starting dose level, then dose escalation will proceed to the second dose level. If ≥ 2 DLTs are observed during the first cycle among the 3 or 6 evaluable patients treated with the initial dose level, then recruitment will be stopped temporarily or definitively until the reasons for this finding have been clarified. If the dose is increased to the second dose level, 3 to 6 evaluable patients will be included, and the 3+3 design rules will be applied again. If ≤ 1 out of 6 evaluable patients experience a DLT during the DLT period at the second dose level, this dose will be considered as the optimal dose level i.e., the RP2D. If ≥ 2 evaluable patients experience a DLT during the DLT period at the second dose level, the initial dose level will then be declared the RP2D. Once the RP2D is defined, any patient still receiving treatment can be switched to the RP2D, if deemed appropriate by the Investigator and agreed by the sponsor.

The sample size will be determined by the number of patients included per dose level and the observed toxicities. Given that (i) a maximum number of two dose levels will be explored, (ii) a classical 3+3 design will be used and (iii) at least 6 patients need to be treated at the RP2D before the phase II part starts formally, between 3-12 evaluable patients will be included. Patients non-evaluable for DLT will be replaced as appropriate.

4.1.2. PART B

Part B is a multicenter, open-label, basket trial using Debio 1143 in combination with nivolumab at the RP2D as previously defined in Part A, in patients with advanced/unresectable solid tumours. Eligible patients will be simultaneously included into four cohorts according to tumour type:

- Cohort 1: Small cell lung cancer (SCLC; including extrapulmonary small-cell carcinomas or large cell neuroendocrine lung carcinoma, as per World Health Organisation [WHO] Classification of Lung Tumors of 2015)
- Cohort 2: Squamous Cell Carcinoma of the Head and Neck (SCCHN; nasopharyngeal carcinomas are excluded)
- Cohort 3: Gastrointestinal (GI) cancers, including oesophageal, gastric, colorectal or pancreatobiliary tumours, with known microsatellite instability-high (MSI-H)/ mismatch repair deficiency (MMRd) or other known deoxyribonucleic acid (DNA) damage response (DDR) abnormalities (incl. homologous

Document: T:\sas\Debiopharm\Debio_1143\CZA60507\Biostatistics\Documentation\SAP\SAP Text\V5

Author: XXXXXXXXXX Version Number: 5.0
Version Date: 19APR2022

Template No.: CS_TP_BS016 Revision 5
Effective Date: 01Apr2018

Reference: CS_WI_BS005

recombination deficiency [HRD]).

- Cohort 4: platinum-resistant epithelial ovarian cancer (EOC), endometrial cancer, primary peritoneal cancer (PPC) and cervical cancer, with known MSI-H/MMRd, hereditary/somatic mutations of the breast cancer type 1 (BRCA1) and BRCA type 2 (BRCA2) genes or other known DDR abnormalities (incl. HRD).

The primary objective of Part B is to assess whether the combination of Debio 1143 with nivolumab is active overall and in each cohort. Early futility stopping rules based on ORR (unconfirmed) will be used. In each cohort, if no unconfirmed response is observed according to Response Evaluation Criteria in Solid Tumors (RECIST v1.1) or Gynecologic Cancer Intergroup (GCIg) criteria (Cohort 4, if applicable) once the initial 8 evaluable patients have been assessed at least twice after baseline or have discontinued their treatment earlier, futility will be concluded and recruitment will be stopped in that cohort. If at least one response (unconfirmed) is documented in the initial 8 evaluable patients, recruitment shall continue up to 11 evaluable patients. At least two unconfirmed responses must then be observed in these 11 evaluable patients to continue the recruitment up to 15 evaluable patients in that cohort.

The total sample size will be between 32 (if all cohorts are futile) and 60 evaluable patients (if none of the 4 cohorts is futile). If a patient is not evaluable (i.e. not included in efficacy analysis set) he/she will be replaced.

In Part B, patients will receive Debio 1143 at the RP2D established in Part A, in combination with nivolumab at the standard dose. Per-patient dose adjustments of Debio 1143 will be considered according to the severity of any eventual observed toxicity.

Participants are planned to be treated with Debio 1143 and nivolumab for up to 52 weeks (i.e., 13 cycles, until any of the following events occurs: symptomatic progressive disease (PD), asymptomatic but confirmed PD (as per iRECIST), unacceptable toxicity (per Investigator judgment and despite up to two dose adjustments), patient withdrawal, or treatment delay greater than 4 and 8 weeks (+1 week tolerance) for Debio 1143 and nivolumab, respectively.

Permission to prolong the study treatment for one additional year can be exceptionally granted by the Sponsor, if patients are deriving continuous clinical benefit from the study treatment. Medical justification for extending the treatment and the assessment of the risk/benefit balance must be provided by the Study Investigator and will be discussed with the Sponsor. The decision to further extend study treatment will be re-evaluated on a yearly basis for each patient.

4.2. SCHEDULE OF EVENTS

Schedule of events can be found in Section 8.3.1 of the protocol.

Document:	T:\sas\Debiopharm\Debio_1143\CZA60507\Biostatistics\Documentation\SAP\SAP Text\V5	Version Number:	5.0
Author:	██████████	Version Date:	19APR2022
Template No.:	CS_TP_BS016 Revision 5	Reference:	CS_WI_BS005
Effective Date:	01Apr2018		

Copyright © 2009, 2010, 2012, 2016, 2018 IQVIA. All rights reserved. The contents of this document are confidential and proprietary to IQVIA Holdings Inc. and its subsidiaries. Unauthorized use, disclosure or reproduction is strictly prohibited.

4.3. CHANGES TO ANALYSIS FROM PROTOCOL

Screened Analysis Set

The protocol does not mention a screened analysis set but it has been included in this SAP for the purposes of subject disposition analyses.

Analysis of primary endpoint (ORR)

The protocol mentions reporting ORR at final analysis in terms of relative and absolute frequencies along with a 95% confidence interval. As this is a Bayesian analysis, we need to provide an estimate of the ORR based on the posterior beta distribution along with a 95% credibility interval. This has been described in section 17.1.3.

Pharmacokinetics

Graphical presentation of concentration-time profiles is simplified to depict geometric mean concentrations \pm geometric standard deviations and individual profiles on log₁₀/linear scales.

For the non-compartmental PK analysis, in addition to the analysis for plasma Debio 1143 and Debio 1143-MET1 described in the protocol, PK parameters will also be calculated for serum nivolumab.

Additional descriptive statistics, in addition to the ones specified in the protocol, are included for concentration and PK parameter summaries for consistency with data presentation in previous study. For the list of all descriptive statistics, refer to section 7.6.

Efficacy Analysis Set

As per protocol, treatment failure is defined as any of the following: death, unacceptable toxicity, clinical deterioration and/or symptoms worsening. Treatment failure definition is updated and defined as any: death, unacceptable toxicity, clinical deterioration and/or symptoms worsening, *except those linked to COVID-19*.

The following category is not described in the protocol:

Category 7: Patients whose treatment had to be delayed or interrupted for reasons related to COVID-19 pandemic only and did not receive at least 25% of the planned Debio1143 dose or skipped one nivolumab infusion during cycle 1. Exposure during the first 3 treatment cycles will also be considered as part of the assessment of patients who fall into this category. Planned analysis

Due to the futility of the part B cohorts, no pooling of part A and Part B will be performed.

Document: T:\sas\Debiopharm\Debio_1143\CZA60507\Biostatistics\Documentation\SAP\SAP Text\V5

Author: XXXXXXXXXX Version Number: 5.0
Version Date: 19APR2022

Template No.: CS_TP_BS016 Revision 5
Effective Date: 01Apr2018

Reference: CS_WI_BS005

Copyright © 2009, 2010, 2012, 2016, 2018 IQVIA. All rights reserved. The contents of this document are confidential and proprietary to IQVIA Holdings Inc. and its subsidiaries. Unauthorized use, disclosure or reproduction is strictly prohibited.

Another sensitivity analysis will be performed by censoring the OS at the time of death due to COVID-19, which was not planned as per protocol. This will be applicable only if there is at least one death due to COVID-19.

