### 11.6.4. Final analysis

The final analysis will be performed within one year of the End of the Main study period (which lasts until 18 months after LPI or 60 days after last LPLV, whichever occurs first).

Data collected after the Main study period for patients entering the Extended study period, will be summarized using descriptive statistics and included in an addendum to the Final CSR.

The main study results will be presented separately for both study parts. An exploratory analysis will be conducted by pooling demographics, baseline characteristics and safety, data from both study parts. In addition, if homogeneity tests allow, and any specific cohort population is adequately represented in Part A, efficacy data from both study parts may be pooled exploratory, as appropriate.

In Part B, according to the Bayesian posterior probability used in each non-futile cohort at the final efficacy assessment conducted in the 15 evaluable patients, the first proof of efficacy will be claimed if at least four confirmed responses are reported in these 15 evaluable patients. This efficacy boundary was derived assuming a confirmed ORR of 15% and a probability confidence threshold of efficacy of 80%.

A homogeneity test of the primary endpoint will be conducted in the non-futile cohorts showing a confirmed response rate of at least 15%. In case of homogeneous response rates across the cohorts, efficacy data will be pooled and all the efficacy endpoints will be reported overall and by cohort. Otherwise, the efficacy will

be reported by cohort only. The efficacy of the futile cohorts and of the cohorts with less than 15% response rate will be reported separately.

All other endpoints such as demographics, baseline characteristics, safety, PK, PDy, etc. will be presented overall and for each cohort.

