The Bayesian posterior probability will be used to preliminary assess the primary efficacy endpoint: the confirmed ORR as per RECIST v1.1 and/or GCIG criteria, if applicable. The unconfirmed ORR will be used for the early futility stopping rules.

The main metrics of the Bayesian efficacy monitoring via posterior probability are the following:

- Denote θ as the response rate. The prior distribution of θ is: $\theta \sim \text{Beta}(a_0, b_0)$
- Let R be the number of responses in n observations, $R \sim \text{Binomial}(\theta, n)$.
- The posterior distribution of θ given observed r responses and $n-r$ no responses is:

$$\theta | r, n \sim \text{Beta}(a_0+r, b_0+n-r).$$

For futility monitoring, the following decision rules are introduced:

1. Early stopping for futility: let θ_{fut} be the reference response rate for futility monitoring and P_{fut} be the probability confidence threshold for futility. The trial should be stopped early and the treatment is declared inefficacious if

$$\text{Prob}(\theta \leq \theta_{fut} | r, n) > P_{fut}.$$

2. Criterion for declaring efficacy: let $\theta_{eff, final}$ be the reference response rate for declaring efficacy at the final stage, and $P_{eff, final}$ be the probability confidence threshold for final efficacy.

The treatment is declared efficacious at the end of the trial if

$$\text{Prob}(\theta > \theta_{eff, final} | r, n) \geq P_{eff, final}.$$

In this trial, the metrics are the following:

Metric	Value
Reference response rate for futility monitoring (θ_{fut})	0.05

Document: T:\sas\Debiopharm\Debio_1143\CZA60507\Biostatistics\Documentation\SAP\SAP Text\V5

Author: [REDACTED] Version Number: 5.0
Version Date: 19APR2022

Template No.: CS_TP_BS016 Revision 5
Effective Date: 01Apr2018

Reference: CS_WI_BS005

Probability confidence threshold for futility stopping (P_{fut})	0.2
Reference response rate for efficacy ($\theta_{eff,final}$)	0.15 for confirmed ORR and 0.17 for unconfirmed ORR
Probability confidence threshold for declaring efficacy ($P_{eff,final}$)	0.8
Prior distribution for theta: Beta (α_0, b_0)	(0.5, 0.5)
Maximum number of patients per cohort	15

The futility boundaries are described in the table below:

# Patients (inclusive)	# Responses (inclusive) to be considered as non-futile
8, 9 & 10	≥ 1
11, 12, 13 & 14	≥ 2

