5.4. FINAL ANALYSIS FOR THE MAIN STUDY PERIOD

All final, planned analyses identified in this SAP for the Main study period will be performed by IQVIA Biostatistics following Sponsor authorization of this SAP, Sponsor authorization of analysis sets, and Database Freeze .

The final analysis for the Main study period will include all study endpoints and will be performed within one year of the End of the Main study period i.e., 18 months after the last patient in (LPI) or 60 days after the last patient last visit (LPLV), whichever occurs first . The main study results will be presented separately for both study parts. Only data collected during the Main study period will be included in the final analysis of the Main study period.

Document: T:\sas\Debiopharm\Debio_1143\CZA60507\Biostatistics\Documentation\SAP\SAP Text\5
 Author: ██████████ Version Number: 5.0
 Version Date: 19APR2022

Template No.: CS_TP_BS016 Revision 5 Reference: CS_WI_BS005
 Effective Date: 01Apr2018

Copyright © 2009, 2010, 2012, 2016, 2018 IQVIA. All rights reserved. The contents of this document are confidential and proprietary to IQVIA Holdings Inc. and its subsidiaries. Unauthorized use, disclosure or reproduction is strictly prohibited.

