9. OUTPUT PRESENTATIONS

Appendix 1 shows conventions for presentation of data in outputs.

The templates provided with this SAP describe the presentations for this study and therefore the format and content of the summary tables, figures, and listings to be provided by IQVIA Biostatistics.

All endpoints such as demographics, baseline characteristics, safety, PK, PDy, etc. will be presented overall and by dose level for Part A and cohort for Part B.

All outputs will be presented for both Part A and Part B separately.

For Part B, the efficacy outputs will be reported by cohort.

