18. SAFETY OUTCOMES

All outputs for safety outcomes will be based on the SAF analysis set except the DLT summaries and listing which will be on the RP2D analysis set.

Document: T:\sas\Debiopharm\Debio_1143\CZA60507\Biostatistics\Documentation\SAP\SAP Text\V5

Author: XXXXXXXXXX Version Number: 5.0
Version Date: 19APR2022

Template No.: CS_TP_BS016 Revision 5
Effective Date: 01Apr2018

Reference: CS_WI_BS005

Copyright © 2009, 2010, 2012, 2016, 2018 IQVIA. All rights reserved. The contents of this document are confidential and proprietary to IQVIA Holdings Inc. and its subsidiaries. Unauthorized use, disclosure or reproduction is strictly prohibited.

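### SAP 4.3 cancels all Part A and Part B pooling because of futility, and so drops a pooled safety summary that the protocol plans without condition and that futility does not affect

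*SAP*

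**What the plan says.** Protocol 11.6.4 reports the main results by part and then makes two separate statements about pooling.

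- On demographics, baseline and safety: "An exploratory analysis will be conducted by pooling demographics, baseline characteristics and safety, data from both study parts". No condition is attached.
- On efficacy: "if homogeneity tests allow, and any specific cohort population is adequately represented in Part A, efficacy data from both study parts may be pooled exploratory". This is permissive and carries two conditions.

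SAP 4.3, which lists changes from the protocol, has one sentence on the subject: "Due to the futility of the part B cohorts, no pooling of part A and Part B will be performed". It does not say which data it covers, and futility is its only reason.

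The rest of the SAP follows the broad reading. Section 5.4 keeps the protocol's statement on separate reporting ("The main study results will be presented separately for both study parts") but not the pooling statement that comes next in the protocol. Section 9 adds: "All outputs will be presented for both Part A and Part B separately". Section 18 names the analysis sets for safety ("All outputs for safety outcomes will be based on the SAF analysis set except the DLT summaries and listing which will be on the RP2D" set) and specifies no summary across the two parts.

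**The concern.** The reason given fits one of the two pooling provisions and is applied to both. If the Part B cohorts are futile, there is little point in pooling efficacy with Part A. It does not follow that adverse events should go unpooled. When the efficacy result is negative, the safety of the combination is a large part of what the trial can still report, and the database is small. What is at stake is a combined rate, with its interval, for patients who received the same combination in the two parts, and the matching combined description of who they were.

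**Working it through.** **1. Does the SAP sentence reach beyond efficacy?** Taken alone, SAP 4.3 could be read as concerning efficacy only. Section 9 rules that out. It first says that demographics, baseline, safety and other endpoints are shown overall and by dose level (Part A) or cohort (Part B), and then puts all outputs under separate parts. Overall therefore means overall within a part. With no pooled output in sections 5.4 or 18, the pooled demographics, baseline and safety summaries are gone.

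**2. Does futility contain anything about safety?** Both documents define it the same way: "The unconfirmed ORR will be used for the early futility stopping rules". A cohort stops if Pr(θ ≤ 0.05 | r, n) > 0.2 under a Beta(0.5, 0.5) prior, so the posterior is Beta(0.5 + r, 0.5 + n − r). The plan's boundaries reproduce:

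| Responses / evaluable | Pr(θ ≤ 0.05) | Decision |
|---|---|---|
| 0/8 | 0.643 | stop |
| 1/8 | 0.149 | continue |
| 1/11 | 0.224 | stop |
| 2/11 | 0.042 | continue |

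The only inputs are the response count and the number evaluable.

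**3. Does the protocol let futility limit safety reporting elsewhere?** No. In protocol 11.6.4, futile cohorts are kept out of the pooled Part B efficacy analysis, but for the rest: "All other endpoints such as demographics, baseline characteristics, safety, PK, PDy, etc. will be presented overall and for each cohort". The protocol itself separates the two.

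**4. What does the missing summary cost?** Inputs from protocol 11.1: the first futility look is at 8 and the second at 11 evaluable patients per cohort, with four cohorts and at least 6 patients at the RP2D in Part A.

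- All cohorts stop at the first look: 4 × 8 = 32 in Part B; 32 + 6 = 38 pooled.
- All cohorts stop at the second look: 4 × 11 = 44 in Part B; 44 + 6 = 50 pooled.

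If no event of a given type is seen in n patients, the one-sided 95% upper bound on its rate is 1 − 0.05^(1/n):

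| Scenario | Part B alone | Part B + 6 from Part A | Reduction |
|---|---|---|---|
| All stop at 8 | n=32: 8.9% | n=38: 7.6% | about 1.4 points |
| All stop at 11 | n=44: 6.6% | n=50: 5.8% | about 0.8 points |

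The reductions are taken from unrounded bounds (8.94 − 7.58 and 6.58 − 5.82). Assumption: the number treated equals the number evaluable. The documents do not give the numbers treated, and because non-evaluable patients are replaced, the safety set may be larger and the bounds lower.

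**The case against.** The strongest defence is that this is a declared change to an analysis that the protocol itself calls exploratory. Protocol 11.6 makes the SAP the definitive plan and allows a different analysis. The change appears in the SAP section meant for changes and in its version history. All of that stands: nothing is concealed and no primary or secondary objective depends on the pooled tables. But protocol 11.6 ties a change to circumstances that make the planned analysis unsuitable, or to better methods, and futility is neither for safety data.

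Separate reporting could also be defended on substance. Part A has extra Day 3 and Day 17 visits, US sites join only in Part B, measurable disease is required only in Part B, and Part A may include a second dose level. These are fair reasons for care in reading a pooled table. The SAP cites none of them, and showing results by starting dose deals with the last.

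A reader might infer more than the documents support:

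- *That splitting the tables makes uncommon events less likely to be seen.* It does not. With 32 + 6 = 38 patients treated, the chance of at least one event with a true rate of 5% is 1 − 0.95^38 = 85.8%, whether they appear in one table or two. Part A events remain in the safety tables and in the listings of adverse events, serious events and events leading to death.
- *That the Part B safety objective is no longer met.* It concerns the RP2D in the basket trial, and Part B safety tables, overall and by cohort, answer it.
- *That all 12 possible Part A patients would add to RP2D safety.* Twelve means six at each of two dose levels, so such a pool mixes doses.

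**Conclusion.** The point holds in a limited form. The SAP removes a planned, unconditional, exploratory combined summary for a reason that bears only on efficacy. What is lost is the combined rate and interval. Some counts can be added by hand from the two sets of tables, but medians, other quantitative summaries and intervals cannot.

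The size is modest: a zero-event upper bound higher by about 0.8 to 1.4 percentage points than it would be with pooling. The range runs from all cohorts stopping at 11 to all stopping at 8, and a mixture falls between. It assumes that treated equals evaluable, that 6 Part A patients received the RP2D, and that the SAP's reference to futility covers all four cohorts; the SAP does not say at which look each one stopped. The change should be made because it is cheap and brings the SAP back into line with the protocol, not because any conclusion of the trial is at risk.

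**What to change.** 1. In SAP 4.3, limit the sentence to efficacy data.
2. Restore the protocol's pooled demographics, baseline and safety summaries across both parts, in section 5.4 and the relevant output sections. Show them by Debio 1143 starting dose, so that patients who started at the RP2D can be read separately if Part A includes another dose level. The protocol does not ask for this split; it is added to keep dose levels apart.
3. Add the matching exception to the statement in SAP section 9 that all outputs are separate by part.
4. Footnote the pooled tables to say that Part A had extra Day 3 and Day 17 visits.

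If the sponsor still prefers separate reporting only, SAP 4.3 should give a reason that concerns safety data.

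The cost is SAP wording and a few more outputs, or a pooled column, from existing programs. No new data are needed.
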